The optional long-term extension period will allow eligible subjects who complete Part B of Study JPDA to receive up to an additional 52 weeks of LY3337641. Subjects who complete the 12-week dosing period of Study JPDA Part B and who, in the opinion of the investigator, have no condition that would preclude continued participation in the study, will be eligible to participate in the extension. The last visit of the dosing period of Study JPDA Part B (Week 12, Part B) will also serve as the initial visit for the extension (Week 12, extension). Subjects who decide to participate in this addendum will not have the 2-week post-treatment safety follow-up period visit in Part B, but will enter the long-term extension period instead and have their 2-week safety follow-up visit at the end of the long-term extension period (Visit 805). Subjects will sign a separate informed consent form to enroll in the long-term extension period.

All subjects originally randomized to any dose of LY3337641 in Study JPDA Part B will continue on their current dose in the long-term extension. All subjects originally randomized to placebo in Study JPDA Part B will be rerandomized at the initial visit of the extension (Week 12) in a 1:1:1 ratio to receive 5, 10, or 30 mg of LY3337641. The entire long-term extension period will remain double-blind, as the dose of LY3337641 will remain blinded to the site and subjects. This addendum is considered unblinded to the sponsor once the main study is unblinded (see [Figure JPDA.5.2](#)).

Part A

[figure not shown]

Part B

Note: There will be an interim unblinded safety analysis by an assessment committee at least 2 weeks after all subjects have had their last dose in Part A. If a decision to proceed with the study is made, Part B will start enrolling new subjects. Part A subjects cannot participate in Part B.

Figure JPDA.5.1. Illustration of the study design for Clinical Protocol I8K-MC-JPDA.

*At Weeks 16 and 20, subjects who achieve at least a 20% improvement from baseline in either the tender or swollen joint count will be considered responders. Subjects who do not achieve response to study drug by this criterion will be eligible for rescue therapy. Starting at Week 24, rescue therapy may be implemented for any subject determined to have ongoing active disease as assessed by the investigator.

Figure JPDA.5.2. Illustration of the study design for optional long-term extension addendum of Clinical Protocol I8K-MC-JPDA(1).

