6.1.2. Baseline Definition

The baseline will be defined as the last available value before the first administration of study drug for both efficacy analyses, including unscheduled measurements for both parts separately. In most cases, this will be the measure recorded on Study Day 1 (Visit 2 in Part A and Visit 102 in Part B). Change from baseline values will be calculated as the postbaseline value minus the baseline value for each scheduled postbaseline time point. If the baseline value is missing (ie, no screening values, no Day 1 value, and no unscheduled measurements), the change from baseline will be missing as well.

For safety analyses, the baseline includes all pre-existing conditions recorded and any adverse events (AE) recorded before the first dose of study drug. Detailed definitions for each period of the studies are described in Section 6.4.2.

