6.1.3. Missing Data Imputation

6.1.3.1. Non-Responder Imputation (NRI)

All subjects who discontinue the study or permanently discontinue the study treatment at any time for any reason will be defined as nonresponders for the NRI analysis for categorical variables, such as ACR20/ ACR50/ ACR70, from the time of discontinuation and onward. If, at the time of study database lock, there are subjects with unresolved interruptions of study drug (ie, not yet re-started, to be confirmed as a temporary interruption, and not yet permanently discontinued), these subjects will be treated as having been permanently discontinued from study drug for the purposes of data imputation for analysis purposes.

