6.5.5. Analyses for the Optional Long-Term Extension Period

The objective of the optional long-term extension period is to collect long-term safety and efficacy data on LY3337641. For all subjects entering the long-term extension, the baseline visit is defined as Visit 106 in Part B.

Subjects will be grouped according to the treatment group in long-term extension and randomized treatment in Part B:

LY5mg(LTE)_Placebo(Part B); LY5mg(LTE)_LY5mg(Part B);

LY10mg(LTE)_Placebo(Part B); LY10mg(LTE)_LY10mg(Part B);
LY30mg(LTE)_Placebo(Part B); LY30mg(LTE)_LY30(Part B)

Unless otherwise specified, efficacy and health outcomes analyses will be conducted on the mITT population, defined as all randomized subjects receiving at least 1 dose of study drug. The analysis population (for applicable treatment outcome measures) will be all subjects with both a baseline and at least 1 postbaseline data measurement.

All variables and the change from baseline will be summarized by descriptive statistics. The statistics for continuous variables include mean, median, standard deviation, and number of observations. Categorical variables will be summarized by counts and percentages. No statistical hypothesis testing will be performed. The efficacy and health outcomes will be summarized as described in Section 6.3.

Safety analysis will be performed for all subjects entering the LTE, receiving at least 1 dose of the study drug and who do not discontinue the study for the reason “Lost to Follow-up” at the first postbaseline visit in LTE. The safety analysis will be conducted as described in Section 6.4. Duration of exposure will be calculated for each subject entering the LTE and summarized by treatment group for LTE period and cumulatively from Part B. Subjects who do not achieve response to study drug are eligible for rescue therapy at Week 16 and Week 20. From Week 24 onward, rescue therapy may be implemented for any subject determined to have ongoing active disease as assessed by the investigator. The safety, efficacy, and health outcome measures will be summarized separately for subjects who receive rescue therapies as described in Section 6.3 and Section 6.4.

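### Extension response rates (SAP 6.5.5) can be distorted: rescue has no scoring rule, and a Visit 106 baseline can class maintained responders as nonresponders

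*SAP*

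**What the plan says.** **Reporting of the extension (SAP 6.5.5).** Collecting long-term efficacy data is part of the extension's objective. Subjects are grouped into six sequences of Part B and extension treatment, with no hypothesis testing. On the population: "efficacy and health outcomes analyses will be conducted on the mITT population, defined as all randomized subjects receiving at least 1 dose of study drug". Efficacy is summarised by the methods of SAP 6.3. On rescue: "The safety, efficacy, and health outcome measures will be summarized separately for subjects who receive rescue therapies as described in Section 6.3". The section does not say whether rescued subjects also stay in the six main groups, or how their response is scored.

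**Who is rescued.** SAP 6.5.5: "Subjects who do not achieve response to study drug are eligible for rescue therapy at Week 16 and Week 20". From Week 24, "rescue therapy may be implemented for any subject determined to have ongoing active disease as assessed by the investigator". The response rule for Weeks 16 and 20 is given in the note to Figure JPDA.5.2 (SAP 5.1): "subjects who achieve at least a 20% improvement from baseline in either the tender or swollen joint count will be considered responders".

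**Baseline.** SAP 6.5.5: "For all subjects entering the long-term extension, the baseline visit is defined as Visit 106 in Part B". SAP 6.1.2 gives the general definition: "The baseline will be defined as the last available value before the first administration of study drug".

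**Imputation.** The nonresponder rule (NRI, SAP 6.1.3.1) reads: "All subjects who discontinue the study or permanently discontinue the study treatment at any time for any reason will be defined as nonresponders". The modified carry-forward rule (mLOCF, SAP 6.1.3.2) covers discontinuation and missed visits. Neither mentions rescue.

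**The concern.** Rescue is offered because a subject has not responded or still has active disease, so it is an outcome of treatment. A summary that sets rescued subjects apart selects on that outcome. A summary that keeps them without a rule credits any improvement after rescue to the study drug. The SAP does not say which it intends.

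The baseline raises a separate problem. SAP 5.1 has subjects randomised to LY3337641 in Part B continue on the same dose, so for them Visit 106 comes after 12 weeks of treatment. Percent improvement from that visit measures further gain and does not show whether the response has lasted. If the Week 16/20 rule uses the same visit, it also decides who becomes eligible for rescue, and so who enters the separate summary.

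At stake is whether a reader can interpret a long-term response percentage at all, given an unstated denominator, an unstated scoring rule and a reference visit that changes meaning between former placebo and continuing subjects.

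**Working it through.** The plan states no rescue rate, response rate or sample size for the extension, so there is no extension figure to reproduce. The rates below are assumptions, shown as ranges. The 55% matches the active-arm rate implied by the Part B sample-size section (30% + 25 points at Week 12). It is borrowed for illustration and is not an extension estimate.

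**1. Scoring of rescued subjects.** At a given visit let N = entrants in a group, R = rescued, a = non-rescued responders, b = rescued subjects who meet the response criterion after rescue.

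- Rescued left out: a/(N−R)
- Rescued kept, no rule: (a+b)/N
- Rescue counted as nonresponse: a/N

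Since N−R ≤ N and b ≥ 0, the first two are never below the third, whoever is rescued.

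For the exclusion reading, let f = R/N and p = a/(N−R). The third rate is then p(1−f) and the excess is pf. In each cell the first figure is p(1−f) and the second is the excess.

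| f | p = 40% | p = 55% | p = 70% |
|---|---|---|---|
| 10% | 36.0%; 4.0 points | 49.5%; 5.5 | 63.0%; 7.0 |
| 20% | 32.0%; 8.0 | 44.0%; 11.0 | 56.0%; 14.0 |
| 30% | 28.0%; 12.0 | 38.5%; 16.5 | 49.0%; 21.0 |
| 40% | 24.0%; 16.0 | 33.0%; 22.0 | 42.0%; 28.0 |

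**2. Baseline.** SAP 6.3.1 computes percent improvement as (baseline − value) × 100 / baseline. Take tender counts of 20 at Day 1, 8 at Visit 106 and 8 at Week 16.

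- From Day 1: (20 − 8)/20 = 60%
- From Visit 106: (8 − 8)/8 = 0%

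For ACR20, Step 2 of the SAP 6.3.1 algorithm makes a subject a nonresponder if either joint count improves by less than 20%. The tender count alone therefore reclassifies this subject. For the Week 16/20 rule, either count can qualify, so the subject fails only if the swollen count also falls short. If a count is zero at Visit 106, the formula is undefined.

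More generally, a subject improved by a fraction r at Week 12 needs 1 − 0.8(1 − r) improvement from Day 1 to show a further 20% from Visit 106. For r = 20%, 50% and 60% that is 36%, 60% and 68%.

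**3. Does the net effect have a fixed direction?** Take 100 continuing subjects, 55 of them maintained responders from Day 1 and 45 nonresponders.

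| Responders rescued | Nonresponders rescued | Non-rescued rate | Rescue as nonresponse | Ignoring rescue |
|---|---|---|---|---|
| 0% | 50% | 55/77.5 = 71.0% | 55.0% | 55% |
| 50% | 50% | 27.5/50 = 55.0% | 27.5% | 55% |
| 50% | 30% | 27.5/59 = 46.6% | 27.5% | 55% |

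Against rescue as nonresponse, the non-rescued rate is higher in every row. Against the rate that ignores rescue, it can be above, equal or below.

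**The case against.** A reader might infer that the SAP's long-term response rates are inflated, and on any reading. The documents do not support that.

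- A separate summary of rescued subjects may be an additional table. The mITT wording in SAP 6.5.5 excludes nobody for rescue. This stands against the exclusion reading, but it leaves the scoring gap: kept subjects still have no rule for response after rescue.
- The Visit 106 baseline lowers percent-improvement rates in continuing subjects. The two problems can offset each other, as the third row in part 3 of the working shows.
- Counting rescue as nonresponse is one strategy. Reporting outcomes regardless of rescue is another legitimate one for descriptive data. This stands. The first strategy fits the SAP's existing nonresponder approach, but whichever is chosen must be stated.

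A reader might also infer that the figure note contradicts SAP 6.5.5. It does not do so outright. The note sits under study design and the Visit 106 definition under analyses, and a rescue rule need not share the analysis baseline. If the rule means the pre-first-dose value, maintained responders are not misclassified by it. Protocol Addendum 1 governs the extension, is not among the documents and may name the visit, so the gap is shown for the SAP only. Failing the rule only makes a subject eligible for rescue, and the rule applies only at Weeks 16 and 20.

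The Visit 106 baseline for extension response endpoints does not depend on the addendum, because SAP 6.5.5 states it for all entrants and sends efficacy to SAP 6.3.

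**Conclusion.** The point holds as a risk of distortion in the descriptive extension results.

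- **Rescue scoring.** With no rule, the reported rate is at or above the rate with rescue counted as nonresponse. That direction is certain for that comparison only. The size is unknown: 5.5 to 22 points on the exclusion reading with 10% to 40% rescued and a 55% non-rescued rate, and 4 to 28 points if the non-rescued rate is 40% to 70%. All of these rates are assumed.
- **Baseline.** Applied as written, Visit 106 classes continuing subjects who hold their Week 12 response as nonresponders on percent-improvement endpoints. Low disease activity and remission, defined by DAS28-hsCRP thresholds, do not depend on baseline and are not touched by this part.
- **Week 16/20 rule.** The SAP does not identify its reference visit.

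A claim that long-term efficacy is overstated overall would go too far, because the two mechanisms can pull in opposite directions. The extension has no hypothesis tests, and the Week 12 primary analysis is unaffected. The matter should be settled before the extension data are analysed.

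**What to change.** Amend SAP 6.5.5, with a cross-reference in 6.1.3:

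1. Keep all extension subjects in the main treatment-sequence summaries, and label the rescued-subject table as supplementary.
2. Extend NRI so that subjects count as nonresponders from the start of rescue for responder endpoints.
3. State how continuous values after rescue are handled, for example by carrying forward the last pre-rescue value in line with mLOCF.
4. Also report extension response endpoints against the pre-first-dose baseline of SAP 6.1.2. For former placebo subjects, Visit 106 may be shown as well.
5. Reconcile the note to Figure JPDA.5.2, SAP 6.1.2, SAP 6.5.5 and the addendum on the reference visit for the Week 16/20 rule. Which clinical rule is right is for the sponsor to decide.

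The cost is a few sentences and a little more programming. Rates with rescue counted as nonresponse will look less favourable. The change needs a rescue start date. SAP 6.2.4 uses start and stop dates for concomitant therapies, but the documents do not show how rescue is captured in the extension, so this must be confirmed.

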6.6. Interim Analyses

The assessment committee is authorized to evaluate unblinded interim efficacy and safety analyses. Study sites will receive information about interim results ONLY if they need to know for the safety of their subjects.

Unblinding details are specified in a separated unblinding plan.

For Part A, 2 interim analyses are planned. The first interim will take place at least 2 weeks after all subjects have had their last dose. The second will take place when all data from Part A are available. Since all safety data for the primary objective in the Part A Dosing Period will be completed at the first interim, the study team will be unblinded to all available results for both interims in Part A.

For Part B, an interim efficacy analysis is planned when approximately 40% of the subjects have completed the Week 12 visit. This interim analysis will be conducted for internal decision making to trigger planning activities for future studies associated with LY3337641. The study will not be stopped early for efficacy. No adjustment of type I error will be performed. The PK/PD data will also be reviewed as part of the interim analysis to initiate model development processes. Based on emerging data, additional interim analyses may be conducted by an assessment committee to review unblinded safety data.

A second interim analysis in Part B is planned when all subjects in Part B have completed Visit 802 or discontinued early from the study. This interim analysis is planned to be the final analysis for Part B for Clinical study report (CSR) writing. This interim will include all planned analyses of available data. The study team will be unblinded to all available results for Part B.

If the assessment committee determines that an additional efficacy interim analysis may be needed before the Part B final analysis for internal decision-making for future studies, then an additional efficacy interim analysis may be conducted. This study will not be stopped early for efficacy reasons. No adjustment of type I error will be performed. The PK/PD data may be reviewed, and the model may be updated.

Appendix 1. Corticosteroids Conversion

The ATC code H02 will be used to select all possible corticosteroids (H02 Corticosteroids for systemic use with route of Oral). All unique preferred terms in the database falling under the ATC code H02 will be reviewed by the medical group in order to determine which ones should be included. All corticosteroid doses need to be converted to prednisone equivalent doses. If additional conversion factors are required, these will be added to the table below in a SAP prior to database lock.

The following table should be used for converting non-prednisone medications to prednisone equivalent:

Multiply the dose of the corticosteroid taken by the subject (in milligrams) in Column 1 by the conversion factor in Column 2 to get the equivalent dose of prednisone (in milligrams).

Example: Subject is taking 16 mg of methylprednisolone orally daily. To convert to prednisone: 16 mg methylprednisolone X 1.25 = 20 mg prednisone. 16 mg of methylprednisolone taken orally daily is equivalent to 20 mg of prednisone taken orally daily.

Corticosteroid Preferred Term	Conversion factor for converting to an equivalent prednisone dose
PREDNISONE	1
PREDNISONE ACETATE	1
PREDNISOLONE	1
PREDNISOLONE ACETATE	1
PREDNISOLONE SODIUM PHOSPHATE	1
METHYLPREDNISOLONE	1.25
METHYLPREDNISOLONE ACETATE	1.25
METHYLPREDNISOLONE SODIUM SUCCINATE	1.25
TRIAMCINOLONE	1.25
TRIAMCINOLONE ACETONIDE	1.25
TRIAMCINOLONE HEXACETONIDE	1.25
CORTISONE	0.2
CORTISONE ACETATE	0.2
HYDROCORTISONE	0.25
HYDROCORTISONE ACETATE	0.25
HYDROCORTISONE SODIUM SUCCINATE	0.25
BETAMETHASONE	6.25
BETAMETHASONE ACETATE	6.25
BETAMETHASONE DIPROPIONATE	6.25
BETAMETHASONE SODIUM PHOSPHATE	6.25
DEXAMETHASONE	6.25
DEXAMETHASONE ACETATE	6.25
DEXAMETHASONE PHOSPHATE	6.25
DEXAMETHASONE SODIUM PHOSPHATE	6.25
PARAMETHASONE	2.5

Corticosteroid Preferred Term	Conversion factor for converting to an equivalent prednisone dose
DEFLAZACORT	0.83
CELESTONA BIFAS	6.25
DEPO-MEDROL MED LIDOKAIN	1.25
DIPROSPAN	6.25
FLUOCORTOLONE	1
MEPREDNISONE	1.25

References:

Appendix 2. Analytes of Phosphorylated BTK (pBTK)

Total Nucleated Cells Region Events	%pBTK/pITK+ (CD14+)
Region Events Lymphs (TNC)	MEFL pBTK/pITK (CD19+) ^a
%Lymphs (TNC)	MEFL pBTK/pITK (CD14+) ^a
Region Events CD19+ (Lymphs)	Region Events CD3+/CD4+ (Lymphs)
%CD19+ (Lymphs)	%CD3+/CD4+ (Lymphs)
Event Flag CD19+ (Lymphs)	Event Flag CD3+/CD4+ (Lymphs)
Region Events CD14+ (TNC)	%pBTK/pITK+ (CD3+/CD4+) ^a
%CD14+ (TNC)	MEFL pBTK/pITK (CD3+/CD4+) ^a
Event Flag CD14+ (TNC)	Region Events CD3+/CD8+ (Lymphs)
%pPLCy2+ (CD19+) ^a	%CD3+/CD8+ (Lymphs)
%pPLCy2+ (CD14+) ^a	Event Flag CD3+/CD8+ (Lymphs)
MEFL pPLCy2 (CD19+) ^a	%pBTK/pITK+ (CD3+/CD8+) ^a
MEFL pPLCy2 (CD14+) ^a	MEFL pBTK/pITK (CD3+/CD8+) ^a
%pBTK/pITK+ (CD19+)	

^a analytes of interest.

Appendix 3. Analytes of Flow Cytometry

TBNK PANEL	NK PANEL 4
CD3 Cyto-Chex BCT-CL ^a	CD69 NK cells ^a
CD8 Cyto-Chex BCT-CL ^a	CD38 NK cells
CD4 Cyto-Chex BCT-CL ^a	HLA-DR NK cells
CD16+56 Cyto-Chex BCT-CL ^a	CD38HLA-DR NK cells
CD19 Cyto-Chex BCT-CL ^a	CD69 T cells ^a
	CD38 T cells
	HLA-DR T cells
	CD38HLA-DR T cells
	CD69 CD4 T cells ^a
	CD38 CD4 T cells
	HLA-DR CD4 T cells
	CD38HLA-DRCD4 Tcell
	CD69 CD8 T cells ^a
	CD38 CD8 T cells

^a analytes of interest.

All analytes are reported in absolute value and in percentage.

Appendix 4. Lilly-Defined MedDRA Preferred Terms for Herpes Zoster

Preferred Term (MedDRA Version 18.0)	Preferred Term Code
Herpes zoster	10019974
Ophthalmic herpes zoster	10030865
Herpes zoster infection neurological	10061208
Herpes zoster oticus	10063491
Herpes zoster disseminated	10065038
Genital herpes zoster	10072210
Herpes zoster pharyngitis	10074245
Herpes zoster meningoencephalitis	10074248
Herpes zoster meningomyelitis	10074251
Herpes zoster meningitis	10074259
Herpes zoster cutaneous disseminated	10074297
Varicella zoster virus infection	10075611

Appendix 5. Lilly-Defined MedDRA Preferred Terms for Tuberculosis

Preferred Term (MedDRA Version 18.0)	Preferred Term Code
Adrenal gland tuberculosis	10001358
Bone tuberculosis	10056377
Bovine tuberculosis	10006049
Choroid tubercles	10008779
Congenital tuberculosis	10010657
Conjunctivitis tuberculous	10010754
Cutaneous tuberculosis	10011684
Disseminated tuberculosis	10013453
Ear tuberculosis	10014027
Epididymitis tuberculous	10015004
Erythema induratum	10015213
Extrapulmonary tuberculosis	10064445
Female genital tract tuberculosis	10061150
Immune reconstitution inflammatory syndrome associated tuberculosis	10072797
Interferon gamma release assay positive	10072866
Intestinal tuberculosis	10075268
Joint tuberculosis	10056367
Latent tuberculosis	10065048
Lupus vulgaris	10025143
Lymph node tuberculosis	10025183
Male genital tract tuberculosis	10061234
Meningitis tuberculosis	10027259
Mycobacterium tuberculosis complex test positive	10070325
Oesophageal tuberculosis	10030200
Pericarditis tuberculous	10055069
Peritoneal tuberculosis	10053583
Prostatitis tuberculous	10064743
Pulmonary tuberculoma	10066927
Pulmonary tuberculosis	10037440
Renal tuberculosis	10038534
Salpingitis tuberculous	10039463
Silicotuberculosis	10068876
Spleen tuberculosis	10041640
Thyroid tuberculosis	10043774
Tuberculin test positive	10044728

Preferred Term (MedDRA Version 18.0)	Preferred Term Code
Tuberculoma of central nervous system	10052883
Tuberculosis	10044755
Tuberculous abscess central nervous system	10052884
Tuberculosis bladder	10044758
Tuberculosis gastrointestinal	10061390
Tuberculosis liver	10058120
Tuberculosis of central nervous system	10061391
Tuberculosis of eye	10044819
Tuberculosis of genitourinary system	10044828
Tuberculosis of intrathoracic lymph nodes	10044846
Tuberculosis of peripheral lymph nodes	10044965
Tuberculosis ureter	10045026
Tuberculous endometritis	10071559
Tuberculous laryngitis	10045072
Tuberculous pleurisy	10045104
Tuberculous tenosynovitis	10059161

Appendix 6. Lilly-Defined MedDRA Preferred Terms for Potential Opportunistic Infections

Preferred Term (MedDRA Version 18.0)	Preferred Term Code
Candida pneumonia	10053158
Respiratory moniliasis	10038705
Gastrointestinal candidiasis	10017938
Oesophageal candidiasis	10030154
Coccidioides encephalitis	10054214
Coccidioidomycosis	10009825
Cutaneous coccidioidomycosis	10068747
Meningitis coccidioides	10027207
Cryptococcal cutaneous infection	10054216
Cryptococcal fungaemia	10067112
Disseminated cryptococcosis	10013439
Gastroenteritis cryptococcal	10011485
Meningitis cryptococcal	10027209
Neurocryptococcosis	10068368
Biliary tract infection cryptosporidial	10067319
Gastroenteritis cryptosporidial	10017899
Cytomegalovirus colitis	10048983
Cytomegalovirus duodenitis	10049014
Cytomegalovirus enteritis	10049074
Cytomegalovirus enterocolitis	10049015
Cytomegalovirus gastritis	10049016
Cytomegalovirus gastroenteritis	10051349
Cytomegalovirus gastrointestinal infection	10052817
Cytomegalovirus gastrointestinal ulcer	10075619
Cytomegalovirus hepatitis	10011830
Cytomegalovirus mucocutaneous ulcer	10065036
Cytomegalovirus myelomeningoradiculitis	10065621
Cytomegalovirus myocarditis	10056261
Cytomegalovirus oesophagitis	10049018
Cytomegalovirus pancreatitis	10049566
Cytomegalovirus pericarditis	10056721
Cytomegalovirus proctocolitis	10049019
Cytomegalovirus urinary tract infection	10051350
Disseminated cytomegaloviral infection	10049075
Encephalitis cytomegalovirus	10014586

Leo Document ID = 93037d28-dc0c-41a2-b04e-4870093b632a

Approver: PPD

Approval Date & Time: 01-Sep-2017 17:34:52 GMT

Signature meaning: Approved
